7.2.9 PROMIS Global Health

An age-appropriate form of the PROMIS Global Health short form will be administered to subjects (or parent proxy) at:

- Screening/Baseline, Week 2, Week 4, Week 6, Week 9, and Week 12 (Flare-up Component).

The adult form will be administered to subjects 15 years and older. For subjects between 8 and 14 years of age, both the pediatric self-completed and the pediatric proxy-completed forms will be administered. The proxy-completed form will be used for analysis unless only the self-completed form is available.

The PROMIS Global Health short form consists of 10 questions on the adult form and nine questions on the pediatric form scored on varying scales. The questions are described in detail in Appendices 8A, 8B, and 8C of the protocol.

For the adult form, Global Physical Health and Global Mental Health scores will be calculated. The Global Physical Health score will be calculated as the sum of scores from questions 3, 6, 7, and 8, and will range from 4 (worse health) to 20 (better health). The Global Mental Health score will be calculated as the sum of scores from questions 2, 4, 5, and 10, and will range from 4 (worse health) to 20 (better health). In the calculation of the Global Physical Health and Global Mental Health scores, the following questions will be rescaled as shown in [Table 3](#).

Table 3. Rescaled PROMIS Global Health Scale Scores

Question(s)	Score	Rescaled Score
7	0	5
	1-3	4
	4-6	3
	7-9	2
	10	1
8 and 10	1	5
	2	4
	3	3
	4	2
	5	1

If a subject is missing any of the contributing scores, the Global Physical Health or Global Mental Health score will not be calculated.

For the pediatric form, only a Total score will be calculated as the sum of scores from the first seven questions and will range from 7 (worse health) to 35 (better health). If a subject is missing some (but not more than three) of the contributing question scores, the Total score will be calculated as the average observed score multiplied by the number of expected question scores. For example, the Total score would be calculated as the average of the non-missing scores x 7.

Global Physical Health and Global Mental Health scores and Total scores will be converted to T-scores for analysis as described in detail in [Appendix 1](#). A T-score of 50 is normal and increments of 10 +/- 1 standard deviation away from the norm. A T-score <50 indicates worse health, while a T-score >50 indicates better health. Note that higher values indicate better health.

T-scores and changes from baseline will be summarized at each scheduled visit with descriptive statistics. Data from adult and pediatric forms will be summarized separately.

7.2.10 Flare-up Pain and Swelling

Flare-up pain and swelling will be assessed at:

- Screening/Baseline, Week 2, Week 4, Week 6, Week 9, and Week 12 (Flare-up Component).

Adults and pediatric subjects 8 years and older will rate the pain associated with their flare-ups using a scale from 0 (no pain) to 10 (worst pain ever experienced). Pediatric subjects less than 9 years old will rate pain using the Faces Pain Scale – Revised (FPS-R), which ranges from 0 (no pain) to 10 (very much pain) in 2-point increments. Swelling associated with flare-ups will be rated on a scale from 0 (no swelling) to 10 (worst swelling ever experienced).

Ratings for pain and swelling and changes from baseline will be summarized at each scheduled visit with descriptive statistics.

7.2.11 Assistive Devices and Adaptations for Daily Living

Subjects will be given a list of FOP assistive devices and adaptations grouped into 12 categories and asked to select those they use for daily living. The assessment will occur at:

- Screening/Baseline, Week 6, and Week 12 (Flare-up Component).

The use of assistive devices and adaptations will be summarized overall and by category at each scheduled visit with counts and percentages of flare-ups. The number of devices and adaptations used will be summarized overall and by category at each scheduled visit with descriptive statistics.

The use of new-onset assistive devices and adaptations will be summarized overall and by category with counts and percentages of flare-ups. New-onset assistive devices and adaptations are defined as assistive devices and adaptations used at a post-baseline visit that were not used at baseline.

7.2.12 Cartilage, Bone, Angiogenesis, and Inflammation Biomarkers

Blood and urine samples for cartilage, bone, angiogenesis, and inflammation biomarkers will be collected at:

- Screening/Baseline, Week 2, Week 4, Week 6, and Week 12 (Flare-up Component).

Bone and cartilage biomarkers include osteocalcin, bone specific alkaline phosphatase (B-ALP), procollagen type I C-terminal propeptide (PICP), procollagen 1 N-terminal propeptide (PINP), CD retinoic acid-sensitive protein (CD-RAP), and C-terminal telopeptide (CTX). The angiogenesis biomarker is the ratio of fibroblast growth factor and urine creatinine.

Inflammation biomarkers include erythrocyte sedimentation rate (ESR), C reactive protein (CRP), interleukin 6 (IL-6), interleukin 1 beta (IL-1 beta), tumor necrosis factor (TNF), creatine kinase (CK), and lactate dehydrogenase (LDH).

Biomarkers values and changes from baseline will be summarized at each scheduled visit with descriptive statistics. Note that results obtained locally rather than from the central laboratory will not be used to calculate change from baseline and will be excluded from these summaries. Results captured as “<” or “>” will be rounded up or down accordingly for analysis (eg, “<0.61” will be rounded to 0.60).

Abnormal values at baseline and new-onset abnormal values post-baseline will be summarized with counts and percentages of flare-ups. New-onset abnormal values are defined as values from biomarkers that were normal at baseline and abnormal post-baseline or were abnormal at baseline and abnormal in the opposite direction post-baseline (eg, abnormal low at baseline and abnormal high post-baseline). Note that results obtained locally will be included in these summaries.

The following figures will be generated for the Flare-up Component (note that the unit of analysis is each flare-up):

- Mean biomarker values over time (one figure per biomarker, each figure with one line).

- Mean biomarker values over time by incidence of new HO (one figure per biomarker, each figure with one distinctive line per subgroup [new HO, no new HO]).
- Mean biomarker values over time by baseline edema status (one figure per biomarker, each figure with one distinctive line per subgroup [baseline edema present, baseline edema not present]).
- Biomarker values over time by flare-up (one figure per biomarker, each figure with one distinctive line per flare-up). Flare-ups will be identified in the legend with subject ID, flare-up identifier (eg, Flare A, Flare B), gender, and age.
- Mean percent of normal high biomarker values over time (one figure per biomarker, each figure with one line). Percent of normal high = $100 \times \text{value} / \text{upper limit of normal range}$.
- Mean percent of normal high biomarker values over time by incidence of new HO (one figure per biomarker, each figure with one distinctive line per subgroup [new HO, no new HO]).
- Mean percent of normal high biomarker values over time by baseline edema status (one figure per biomarker, each figure with one distinctive line per subgroup [baseline edema present, baseline edema not present]).
- Percent of normal biomarker values over time by flare-up (one figure per biomarker, each figure with one distinctive line per flare-up). Flare-ups will be identified in the legend with subject ID, flare-up identifier, gender, and age.

7.2.13 Duration of Active Symptomatic Flare-up

Subjects will keep a daily diary during the Flare-up Component where the question “Is your flare-up ongoing today?” is answered. Subjects with at least 80% of diary data (at least 67 days with non-missing data) will be used for analysis.

The number of symptomatic days will be calculated as the number of days where the diary question is answered “Yes”. The number of symptomatic days will be summarized with descriptive statistics.

The status of the flare-up will be determined at Week 6 and Week 12. If there are no symptomatic days recorded in the diary, the flare-up will be considered “Resolved prior to the first dose of study drug”. If the last symptomatic day recorded in the diary is on or before the specified visit and is followed by at least one asymptomatic day (ie, diary question is answered “No”), the flare-up will be considered “Resolved”. If the last symptomatic day recorded is on the last diary entry, the flare-up will be considered “Not resolved”. The status of the flare-up will be summarized at Week 6 and Week 12 with counts and percentages of subjects or flare-ups as appropriate.

The days to flare-up resolution will be calculated as follows:

- If the flare-up was considered “Resolved prior to the first dose of study drug”, days to flare-up resolution = 0.
- If the flare-up was considered “Resolved”, days to flare-up resolution = date of flare-up resolution – date of first dose + 1, where the date of flare-up resolution is the last symptomatic day.

- If the flare-up was considered “Not resolved”, days to flare-up resolution = date of last diary entry – date of first dose + 1.

The days to flare-up resolution will be summarized with descriptive statistics.

8 Safety Data

Adverse events will be presented for the Enrolled Population as described in [Section 8.1](#). Safety assessments at Flare-up Component visits will generally be presented in total for the Treated Population. Safety assessments at Follow-up Component visits will be listed.

8.1 Adverse Events

Adverse events (AEs) will be recorded from the time informed consent is signed through study completion. All AEs will be coded to body system and preferred term using the Medical Dictionary for Regulatory Affairs (MedDRA) Version 17.0. At least possibly related AEs are defined as AEs assessed by the Investigator as possibly, probably, or definitely related to study drug. Adverse events that require Common Terminology Criteria for Adverse Events (CTCAE) grading as indicated on the eCRF are considered to be retinoid-associated AEs.

Adverse events with start date on or after Flare-up Study Day 1 and on or before the date of completion for the Flare-up Component will be attributed to the Treatment Period. Adverse events with start date on or after Study Day 1 that are not attributed to the Treatment Period will be attributed to the Non-Treatment Period.

For the Untreated Population, AEs will be summarized in total (note, these are all Non-Treatment Period AEs). For the Treated Population, AEs will be summarized by period (Non-Treatment Period AEs and Treatment Period AEs) and in total. For the Enrolled Population, AEs will be summarized for the Non-Treatment Period and in total.

The incidence of the following AEs will be summarized with counts and percentages of subjects (overview and also by MedDRA body system and preferred term):

- Any AEs
- Any AEs by maximum severity
- Any AEs at least possibly related to study drug
- Any AEs at least possibly related to study drug by maximum severity
- Any retinoid-associated AEs
- Any retinoid-associated AEs by maximum CTCAE grading
- Any serious adverse events (SAEs)
- Any AEs leading to dose modification or interruption of study drug
- Any AEs leading to discontinuation of study drug
- Any AEs leading to discontinuation of study

Data listings will be provided for (1) all AEs, (2) SAEs, (3) AEs leading to dose modification or interruption of study drug, (4) AEs leading to discontinuation of study drug, and (5) AEs leading to discontinuation of study. Study Day and/or Flare-up Study Day for AE start and stop dates will be included on AE listings as appropriate.

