2.3 Study Design

Study PVO-1A-202 Part A is a Phase 2, multicenter, event-based, open-label extension of Study PVO-1A-201. This open-label extension will give subjects who completed Study PVO-1A-201 the opportunity to be followed for up to an additional 36 months, and receive open-label palovarotene should they experience up to two, new, distinct flare-ups.

All enrolled subjects will participate in the **Follow-up Component** of the study. The Follow-up Component will include visits at Study Screening and Study Months 6, 12, 18, 24, 30, and 36. Study Day 1 will be the date of informed consent. Visit windows are +/- 2 weeks. Assessments related to flare-ups during the Follow-up Component will be evaluated at the original flare-up site from Study PVO-1A-201.

Subjects who experience an eligible flare-up will participate in the **Flare-up Component** of the study. The Flare-up Component will include visits at Flare-up Screening and Flare-up Weeks 2, 4, 6, 9, and 12. Flare-up Day 1 will be the date of first dose of study drug for the flare-up. Visit windows are +/- 3 days. Assessments related to flare-ups during the Flare-up Component will be evaluated at new flare-up sites from Study PVO-1A-202 Part A. Note that subjects may have more than one unique new flare-up and that each flare-up will be assessed and analyzed independently.

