4.5 Per Protocol Population

The Per Protocol (PP) Population will include all subjects in the Efficacy Population with no major protocol deviations that may impact the efficacy assessment. Exclusions from the PP Population will be identified prior to database lock. Analyses based on the PP Population will generally be summarized in total. Note that data collected for new unique flare-ups may use each flare-up as the unit of analysis rather than each subject. The PP Population will be a secondary population for analysis of selected efficacy assessments performed at Flare-up Component visits.

5 Treatment Period and Non-Treatment Period

The Treatment Period is defined as the period of days during the Flare-up Component(s) from Flare-up Study Day 1 through the date of completion of the Flare-up Component (ie, Flare-up Study Day 84). The Treatment Period includes all days during Flare-up Components for subjects in the Treated Population.

The Non-Treatment Period is defined as the period of days outside of the Treatment Period. The Non-Treatment Period includes all days in the study for subjects in the Untreated Population and days before, after, or in between Flare-up Components for subjects in the Treated Population.

6 Subject Data

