7.1 Adverse Events

Adverse events will be recorded from the time informed consent (Part B Study Day 1) is signed through study completion. All AEs will be coded to body system and preferred term using MedDRA Version 17.0. At least possibly related AEs are defined as AEs assessed by the Investigator as possibly, probably, or definitely related to study drug. Adverse events that require Common Terminology Criteria for Adverse Events (CTCAE) grading (Version 4.03, 14 June 2010) as indicated on the eCRF are considered to be retinoid-associated AEs.

Adverse events with start date on or after Flare-up Day 1 and on or before the date of completion for the Flare-up treatment will be attributed to the Flare-up Treatment Period. Adverse events with start date on or after Non-Flare-up Day 1 for which the patient is not undergoing flare-up treatment will be attributed to the Non-Flare Treatment Period. Adverse events with start date on or after Study Day 1 that are not attributed to the flare-up or non-flare-up treatments will be attributed to the Non-Treatment Period.

For the both the Enrolled Population and the Treated Population, AEs will be summarized by period (Non-Treatment Period, Non-Flare Treatment Period, Flare-up Treatment Period) and in total.

The incidence of the following AEs will be summarized with counts and percentages of subjects (overall and by MedDRA body system and preferred term):

- Any AEs
- Any AEs by maximum severity
- Any AEs at least possibly related to study drug
- Any AEs at least possibly related to study drug by maximum severity
- Any retinoid-associated AEs
- Any retinoid-associated AEs at least possibly related to study drug
- Any retinoid-associated AEs by maximum CTCAE grading
- Any retinoid-associated AEs by maximum severity
- Any retinoid-associated AEs by seriousness
- Any serious adverse events (SAEs)
- Any severe/life threatening retinoid-associated AE by maximum CTCAE grading
- Any AEs leading to dose modification or interruption of study drug
- Any AEs leading to discontinuation of study drug
- Any AEs leading to discontinuation of study

Data listings will be provided for (1) all AEs, (2) SAEs, (3) AEs leading to dose modification or interruption of study drug, (4) AEs leading to discontinuation of study drug, and (5) AEs leading to discontinuation of study. Part B Study Day and/or Flare-up Day for AE start and stop dates will be included on AE listings as appropriate.

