7.1 Adverse Events

Adverse events will be recorded from the time informed consent (Part C Study Day 1) is signed through study completion. All AEs will be coded to system organ class and preferred term using will be coded using a current version of MedDRA **Study Drug Related Adverse Events:**

At least possibly related AEs are defined as AEs assessed by the Investigator as possibly, probably, or definitely related to study drug.

Adverse events that require Common Terminology Criteria for Adverse Events (CTCAE) grading (Version 4.03, 14 June 2010) as indicated on the eCRF are considered to be retinoid-associated AEs.

Adverse Events Analysis Periods:

All AEs collected during Part C from the time informed consent is signed are considered as treatment emergent adverse events (TEAEs).

TEAEs will be summarized by period (Non-Treatment Period, Non-Flare-up Treatment Period, and Flare-up Treatment Period, Total Treatment Period) and in total.

a) Flare-up treatment period

Adverse events with start date on or after Flare-up Cycle Day 1 and on or before the date of completion for the Flare-up treatment will be attributed to the Flare-up treatment period.

b) Non-Flare-up Treatment Period

Adverse events with start date on or after first Non-Flare-up dose date in Part C for which the subjects are not undergoing flare-up treatment will be attributed to the Non-Flare-up Treatment Period.

Non-Flare-up Treatment Period is period that subjects taking non-flare-up dose including non-flare-up dose interruption periods. All flare-up cycles are excluded.

c) Non-Treatment Period

Adverse events with start date on or after Study Day 1 that are not attributed to the flare-up or non-flare-up treatments will be attributed to the Non-Treatment Period.

Non-Treatment Period are period that subjects are receiving neither non-flare-up and nor flare-up treatment. In Part C, it is the period starting from Part C Study 1 to the day before first study drug dosing date (regardless of whether non-flare-up or flare-up based treatment), and the period from date of study drug discontinuation to end of study or study discontinuation date.

Adverse Events Summary:

The incidence of the following TEAEs will be summarized with counts and percentages of subjects (overall and by MedDRA system organ class and preferred term):

Adverse Event Variables

Adverse Event Observation Periods

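### Adverse events by treatment period are planned only as crude percentages of subjects; the periods can differ greatly in length, so the columns cannot be read as on-drug versus off-drug risk

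*SAP*

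**What the plan says.** **Part A.** Section 5 defines the Treatment Period as running "from Flare-up Study Day 1 through the date of completion of the Flare-up Component (ie, Flare-up Study Day 84"), once per treated flare-up. For treated subjects the Non-Treatment Period is every other study day, that is "days before, after, or in between Flare-up Components for subjects in the Treated Population". Section 2.3 allows subjects "to be followed for up to an additional 36 months" and at most two treated flare-ups. Section 8.1 assigns each adverse event (AE) to a period by start date. It then says "For the Treated Population, AEs will be summarized by period (Non-Treatment Period AEs and Treatment Period AEs) and in total", and gives the measure: "The incidence of the following AEs will be summarized with counts and percentages of subjects". Exposure (6.8) and participation (6.9) are summarized separately and are not used as AE denominators.

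**Part B.** Section 7.1, for both the Enrolled and Treated Populations: "AEs will be summarized by period (Non-Treatment Period, Non-Flare Treatment Period, Flare-up Treatment Period) and in total". The measure is again subjects with an event.

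**Part C.** Section 7.1: "TEAEs will be summarized by period (Non-Treatment Period, Non-Flare-up Treatment Period, and Flare-up Treatment Period, Total Treatment Period) and in total". Section 7 places the AE presentation on the Enrolled Population.

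The plans do use time-based rates elsewhere. Part B 7.1.1 divides flare-ups, including some reported as AEs, by subject-months of follow-up. Part C 5.8 annualizes the flare-up rate. Neither is applied to the AE categories.

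**The concern.** The chance that a subject has at least one event grows with the time over which events are counted. Two columns of such percentages are comparable only if the time at risk is similar. In Part A it need not be: each treated flare-up contributes 84 days, against the rest of a follow-up that may reach 36 months. A reader of the side-by-side table will naturally compare the columns, and the comparison can point the wrong way. Safety is part of the primary objective in all three parts, and the study has no randomized control, so the by-period AE table will carry weight.

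Parts B and C raise a further denominator question. Their period tables are run on populations that include subjects who never entered a given period. Part B 2.4, for example, records that some adults chose not to take non-flare-up treatment. Neither section 7.1 says whose number divides each period column.

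**Working it through.** The plan states no AE rate or precision figure for this point, so there is nothing of its own to reproduce. The period lengths can be built from its numbers.

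**Inputs from the Part A SAP**
- Treatment Period: 84 days per flare-up (section 5), one or two flare-ups (section 2.3), so T = 84 or 168 days.
- Follow-up: up to 36 months (section 2.3), at 30.5 days per month (section 6.9), so 36 × 30.5 = 1098 days.
- Non-Treatment Period: N = 30.5 × months − T.
- Planned dosing in each flare-up: 14 + 28 = 42 days (section 2.4).

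**Assumptions not in the documents**
- Constant event rates: L off drug, and L × RR throughout the Treatment Period.
- L = 0.05 first events per subject-month for illustration. RR = 2, 3 or 5.

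**Formulas**
- Percentage with an event, Treatment Period: 1 − exp(−L × RR × T).
- Percentage with an event, Non-Treatment Period: 1 − exp(−L × N).
- The first is below the second exactly when RR × T < N, that is when RR < N/T. L cancels, so the break-even point does not depend on the assumed background rate.

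**Results** (percentages are Treatment v Non-Treatment at L = 0.05 per month)

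| Follow-up | Flare-ups | T (days) | N (days) | N/T | RR = 2 | RR = 5 |
|---|---|---|---|---|---|---|
| 36 months | 1 | 84 | 1014 | 12.1 | 24.1 v 81.0 | 49.8 v 81.0 |
| 36 months | 2 | 168 | 930 | 5.5 | 42.4 v 78.2 | 74.8 v 78.2 |
| 24 months | 1 | 84 | 648 | 7.7 | 24.1 v 65.4 | 49.8 v 65.4 |
| 24 months | 2 | 168 | 564 | 3.4 | 42.4 v 60.3 | 74.8 v 60.3 |
| 18 months | 1 | 84 | 465 | 5.5 | 24.1 v 53.3 | 49.8 v 53.3 |
| 18 months | 2 | 168 | 381 | 2.3 | 42.4 v 46.5 | 74.8 v 46.5 |
| 12 months | 1 | 84 | 282 | 3.4 | 24.1 v 37.0 | 49.8 v 37.0 |
| 12 months | 2 | 168 | 198 | 1.2 | 42.4 v 27.7 | 74.8 v 27.7 |

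With no drug effect at all (RR = 1), the first row would read 12.9% v 81.0%. With RR = 3 it reads 33.8% v 81.0%. Expressed as rates, that last case is 0.15 v 0.05 per subject-month, a ratio of 3.0, whatever the period lengths.

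**Dilution inside the Treatment Period.** Of each 84 days, 84 − 42 = 42 are planned without drug. If the excess were confined to dosing days, the average rate ratio over the period would be (42 × RR + 42)/84 = (RR + 1)/2, so a threefold rate on dosing days becomes 2.0 over the period.

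**Parts B and C.** No comparable table can be built. Part B flare-up treatment may be extended beyond 84 days (2.4). Part C treatment restarts for intercurrent flare-ups (2.3), and its per-subject flare-up exposure categories run to more than 24 months (5.9.1). The Part C Non-Treatment Period covers only time before first dose and after discontinuation (7.1). Period lengths will vary between subjects, in a direction the documents do not show.

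**The case against.** **No comparison is planned.** All three SAPs say AEs are summarized by period. There is no test, contrast or decision rule. That stands, and the point concerns how a descriptive table can be read, not an invalid inference.

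**Reversal is not inevitable.** A reader might infer that any real excess would appear as a lower percentage on drug. The documents do not support this. Thirty-six months is a maximum, section 6.9 provides for participation of 6 months or less, and actual follow-up is not given. With two flare-ups over 12 months, a background rate giving 20% over 84 days and a doubled on-drug rate, the Treatment Period shows 1 − 0.8^4 = 59% and the Non-Treatment Period 1 − 0.8^(198/84) = 41%. The excess is visible.

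**Other safety evidence exists.** A reader might also take the period contrast for the only within-study evidence of drug-caused AEs. It is not. Part A 8.1 also plans AEs by investigator-assessed relatedness, retinoid-associated AEs by grade, AEs leading to dose changes or discontinuation, a separate Untreated Population summary, and listings with Flare-up Study Day. Relatedness is judged open-label, however, and the Untreated summary has no time denominator either.

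**Parts B and C are less clear.** The column denominators are unstated rather than shown to be wrong. Part C section 7 also bases the final safety summaries on regulatory safety updates that are not shown and may present AEs differently. Part A already confines its two-period table to treated subjects, so the denominator point does not apply there.

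**Rates will not isolate the drug.** The Treatment Period coincides with a flare-up and possibly glucocorticoid use, and half its planned days are off drug. This is true and limits what the fix can deliver. It does not rescue the crude percentages, which share these problems and add the length imbalance.

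**Conclusion.** The concern holds as a limit on interpretation. As written, the by-period AE tables use crude subject percentages with no time denominator. In Part A the side-by-side columns cannot be read as on-drug versus off-drug risk: the Treatment Period percentage is the lower one unless the rate ratio exceeds about 12.1 (one flare-up) or 5.5 (two) at full follow-up, or 3.4 and 1.2 at 12 months. These thresholds rest on constant event rates and on the SAP's own period lengths, not on the assumed background rate. They are for a single subject's period lengths; a treated group with mixed follow-up will fall between the extremes it contains.

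For Parts B and C the same measure is used and period lengths vary, but neither the size nor the direction of any distortion can be stated from the documents. Since the tables are descriptive and other safety summaries are planned, this is a worthwhile, cheap improvement rather than a correction on which the analysis depends.

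**What to change.** In Part A 8.1, Part B 7.1 and Part C 7.1:

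- For each AE category and period, add events per subject-year in the period, and subjects with a first event per subject-year at risk in the period.
- In Parts B and C, state that each period column counts in its denominator only subjects who spent time in that period.
- Base any statement comparing periods on these rates, and keep the crude percentages as description.
- Add a note in Part A that the Treatment Period includes about 42 planned off-drug days per flare-up and coincides with a flare-up, so the rate contrast is not a pure drug effect.

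The rates need only AE start dates, dosing dates and participation dates, which the plans already use. The cost is a few sentences of SAP text and somewhat longer tables.
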